To investigate in insufficient responders to the COBRA-Slim regimen if accelerated access to a six-month course of anti-TNF therapy (etanercept), is leading to improved remission rates when compared to conventional treatment adaptation according to the COBRA-Slim strategy, 28 weeks after randomization into one of two treatment arms.

Other secondary objectives:

1. To further determine the **clinical efficacy** of accelerated access to etanercept versus the standard COBRA-Slim strategy in terms of remission rates and functionality scales.
2. To compare **radiographic progression** between all treatment schemes.
3. To evaluate the side effects of the given treatments as evaluated according to the regulatory guidelines for marketed products.
4. To evaluate the primary outcome using the DAS28ESR instead of the DAS28CRP.

Other secondary exploratory objectives:

1. To further determine the **clinical effectiveness** of accelerated access to etanercept versus the standard COBRA-Slim strategy.
2. To evaluate treatment response based on a set of **PROs**.
3. Depending on the clinical results of the trial, a **health economic analysis** may be justified. This could be part of a health technology assessment project at KCE. Quality of life data as well as the national number of the participating patients are collected in this trial to facilitate a possible economic analysis.

All secondary and exploratory objectives will be assessed both for the insufficient responder population, as for the complete study population.

Outcome measures/endpoints

Primary outcome measure

Area under the curve of DAS28CRP over 104 weeks (long term effectiveness) in insufficient responders randomized to either COBRA-Slim Bio-Induction or Standard COBRA-Slim Induction.

Main secondary outcome measure

Proportion of insufficient responders achieving remission (DAS28CRP<2.6) 28 weeks after randomization (short term efficacy) to either COBRA-Slim Bio-Induction or Standard COBRA-Slim Induction.

Other secondary outcome measures

The following analyses will be performed in the randomized early insufficient responder population (w8-w32) with or without accelerated access to a six-month course of etanercept. The same analyses will also be performed including the randomized groups of insufficient responders, each completed with an early responder control population.

1. Clinical efficacy:
 - Remission (DAS28CRP<2.6) at w104.
 - EULAR response at 28 weeks after randomization and at w104

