 - HAQ response at 28 weeks after randomization and at w104
2. Radiographic progression: X-ray evolution at w52 and w104 compared to BL as reviewed and evaluated by the central team.
3. Side effects: (S)ARs from BL until w104
4. To evaluate the primary outcome using the DAS28ESR instead of the DAS28CRP.

Other secondary, exploratory outcome measures:

1. Clinical effectiveness:

A) In the randomized early insufficient responder population (w8-w32) with or without accelerated access to a six-month course of etanercept.

Effectiveness:

- AUC of DAS28CRP/DAS28ESR during 28 weeks after randomization
- Time to first remission during 28 weeks after randomization
- Sustained remission = remission for at least 24 weeks (BL-w104).
- Number of treatment changes, number of patients able to follow the protocol, number of patients using biologicals and/or GC at 28 weeks after randomization and at w104.
- Cumulative doses of GC and analgesic use at 28 weeks after randomization and at w104.

B) In the complete study population, including the randomized groups of insufficient responders, each completed with an early responder control population.

Effectiveness:

- Sustained remission = remission for at least 24 weeks (BL-w64, BL-w104, w64-w104).
- Number of treatment changes, number of patients able to follow the protocol, number of patients using biologicals and/or GC throughout the entire study

- Cumulative doses of GC and analgesic use throughout the entire study
- 2. Treatment response in terms of PROs:
 - Patient acceptable symptom state (PASS) and RA Impact of Disease (RAID) at 28 weeks after randomization and at w104
 - PASS at w64 and w104.
 - RAID at w 64, 104.
- 3. Cost-effectiveness:
 - WPAI / EQ5D questionnaire at 28 weeks after randomization and at w104
 - Per-protocol and out-of-protocol medication use as well as the number of outpatient visits and occasional hospitalization

[figure not shown]
Depending on the clinical results of the trial, a health economic analysis may be justified. This could be part of a health technology assessment project at KCE. Quality of life data as well as the national number of the participating patients are collected in this trial to facilitate a possible economic analysis.

3 Study design

Overall design

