Addition of etanercept 50mg Subcutaneous (SC) weekly for a period of 24 weeks in this accelerated access arm as the next treatment adaptation.

If target of LDA is still not reached or maintained minimally 12 weeks after the initiation of etanercept, treatment has to be adapted according to the next step of the CareRA2020 adaptation scheme.

Randomization will be balanced according to time-point of randomization, baseline (BL) disease activity and Anti-Citrullinated Protein Antibody (ACPA) and/or Rheumatoid Factor (RF) status to ensure comparability of the treatment groups with respect to these prognostic variables.

Patients who do not meet the criteria for randomization, during the so-called accelerated access period, will all follow the same CareRA2020 treatment adaptation scheme, further detailed in the protocol.

Further protocol-based treat to target period (w32 until w104):

After w32, patients will continue on the therapy assigned to their treatment. In case LDA is lost or still not reached during this protocol-based treat to target phase, treatment will be adapted

according to CareRA2020 adaptation schedule (table 1 page 28). A next adaptation is only allowed after the previous treatment adaptation has reached its full strength, so minimally after the time period specified for each adaptation step (table 2 page 28).

In accordance with the latest EULAR recommendations patients should be further treated to a target of at least LDA but this can be adapted to remission at the investigators discretion.

The minimal dose of MTX required according to protocol is 15 mg PO per week except in case of documented toxicity, then 7.5 mg PO or parenteral is allowed. In case MTX has to be discontinued, Leflunomide should be given at a dose of 20 mg PO daily or 10 mg PO in case of documented toxicity (see paragraph “Treatment toxicity during study”, page 30).

CareRA2020 adaptation schedule

As a first adaptation, from w4 onwards, MTX should be increased to 20mg weekly PO. The next adaptation steps are summarized in table 1.

One exception is the w32 visit, at which a MTX dose increase is not needed, and one should proceed to the second adaptation step.

After w32, adaptation of MTX or leflunomide is at the investigators discretion, but when LDA is not reached one should proceed to the next adaptation step.

Table 1: protocol defined adaptations

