There will be about twenty recruiting centers and the recruitment rate is expected to be around 18 patients per month. To obtain a total sample of 440 patients we expect the needed enrolment period to be 24 months. Therefore, we schedule the enrolment phase to be open from Q2 2018 until Q2 2020. Recruitment rate will be closely monitored and discussed on with sites in case it is lower than expected. If, however, the needed sample size is not yet reached in 24 months, the recruitment period will be extended.

Based on data from previous research, refusal to participate in this type of pragmatic trial is less than 2%. Therefore, we expect consent rate to be 98%. As stated above, screening/randomization failure rate is estimated at 6%, because there were 21 out of 400 patients eventually not randomized in the CareRA trial (2 due to not meeting inclusion/exclusion criteria, 10 due to practical reasons, 7 due to consent withdrawal and 2 due to loss of contact with patient).

Subject populations

For data analysis, we will define the insufficient responder group as 'the efficacy population' to assess efficacy of the 2 different induction schemes in this specific group.

Patients who do not meet the criteria for treatment adaptation within the accelerated access period will be followed up separately. Using the same randomization procedure as for the w8-w32 insufficient responders, at week 32 these patients will be randomized to two subgroups that will be further treated identically but will each act as a complementary responder subpopulation for one of the two insufficient responder subpopulations to reconstruct two artificial global populations, one with accelerated access to etanercept for w8-w32 insufficient responders and one without.

The entire group of patients will be called 'the effectiveness population' to investigate the effectiveness of the different schemes in a general RA population as a whole.

For both populations, an intention to treat, a per-protocol and safety analysis will be performed:

- An **intention to treat analysis** will include all patients randomized into the study. These patients will be analyzed according to the treatment they are randomized to, irrespective of whether they actually received the treatment.
- A **Per protocol analysis** will include all patients randomized that did follow the initial allocated treatment scheme and had the required adaptations performed according to protocol.

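### Randomly splitting identically treated responders at week 32 adds only noise to the exploratory whole-population mean and risk differences; pooling all responders gives the same contrast with a smaller standard error

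*Combined protocol and SAP*

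**What the plan says.** Section 10, Subject populations, calls the insufficient responders the efficacy population and the entire group the effectiveness population. For the latter, "at week 32 these patients will be randomized to two subgroups that will be further treated identically". Each subgroup complements one insufficient-responder arm, "to reconstruct two artificial global populations, one with accelerated access to etanercept for w8-w32 insufficient responders and one without". The intention-to-treat analysis, planned for both populations, "will include all patients randomized into the study. These patients will be analyzed according to the treatment they are randomized to".

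Section 3, Overall design, confirms that there is one regimen for these patients: "Patients who do not meet the criteria for randomization, during the so-called accelerated access period, will all follow the same CareRA2020 treatment adaptation scheme".

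Section 2 says where the constructed populations are used. For the other secondary outcomes, "The same analyses will also be performed including the randomized groups of insufficient responders, each completed with an early responder control population". Part B of the exploratory effectiveness outcomes is set "In the complete study population, including the randomized groups of insufficient responders, each completed with an early responder control population". A general sentence adds: "All secondary and exploratory objectives will be assessed both for the insufficient responder population, as for the complete study population". Section 10, Secondary outcome analysis, treats every outcome beyond the primary and main secondary as exploratory, reported as an effect size with a 95% confidence interval that serves only to convey uncertainty.

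The plan names no estimator or variance method for the whole-population contrast, and gives no reason for splitting the responders instead of using all of them on both sides.

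**The concern.** The accelerated-access strategy differs from the standard one only for patients who become insufficient responders. A responder receives the same care under either strategy, so any difference between the two responder halves is chance. Building the two populations from separate halves puts that chance difference into the strategy comparison, although its expected value is known to be zero.

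What is at stake is precision. Since the plan uses these intervals to show uncertainty, their width is what the split costs. The outcomes concerned, where they are analysed as mean or risk differences, are remission at week 104, EULAR and HAQ response, radiographic change, and the mean or proportion items in part B of the exploratory outcomes. One further outcome is open to reading: item 4 of the other secondary outcomes ("To evaluate the primary outcome using the DAS28ESR instead of the DAS28CRP") would add an AUC analysis if it is taken to extend to the whole population.

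**Working it through.** **Inputs from Section 10.** 442 screened, 416 entered, 25% insufficient responders (104, leaving 312 responders), 21% dropout to week 104. AUC 351 versus 281, SD 103. Remission 50% versus 80% at 28 weeks after randomisation. The documents give no responder remission rate or responder AUC SD, so both are varied below as assumptions.

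**The plan's own figures reproduce.** 442 × 0.94 = 415.5; 416 × 0.25 = 104; 104 × 0.79 = 82. A two-sample t-test for 351 versus 281 with SD 103 has 80.0% power with 70 completers and 86.0% with 82, as stated. No precision is stated for the whole-population contrast.

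**Formulas.** Let p be the insufficient-responder share, Δ the effect among them and N the total.

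- Target under both approaches: p × Δ.
- Var(pooled) = p² × Var(insufficient-responder difference) + Δ² × p(1 − p)/N. The last term allows for estimating p.
- Var(split) = Var(pooled) + (1 − p)² × Var(difference between responder halves).

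The added term is zero only if responder outcomes do not vary, so pooling is always at least as precise. Only the size of the gain depends on assumptions.

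**Remission at week 104** (50% versus 80% assumed to carry over; N = 416, p = 0.25, unadjusted). Target: 0.25 × 30 = 7.5 points.

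- Insufficient-responder term: 0.0625 × (0.25 + 0.16)/52 = 0.000493.
- Term for p: 0.09 × 0.1875/416 = 0.0000406.
- Pooled SE: √0.000533 = 2.31 points.
- Added term at 80% responder remission: 0.5625 × 2 × 0.16/156 = 0.001154, so the split SE is √0.001687 = 4.11 points.

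| Responder remission (assumed) | Split SE | Pooled SE | Ratio | 95% half-width with 21% dropout, split | Pooled |
|---|---|---|---|---|---|
| 70% | 4.53 | 2.31 | 1.96 | 10.0 | 5.1 |
| 80% | 4.11 | 2.31 | 1.78 | 9.1 | 5.1 |
| 90% | 3.44 | 2.31 | 1.49 | 7.6 | 5.1 |
| 95% | 2.96 | 2.31 | 1.28 | 6.5 | 5.1 |

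SEs and half-widths are in percentage points.

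Simulating this case with 21% dropout (20,000 trials per row) gave mean contrasts of 7.5 to 7.6 (split) and 7.5 (pooled) points. Empirical SDs were 5.11, 4.62, 3.90 and 3.37 against 2.57 to 2.61. Coverage of 95% intervals was 94.7 to 96.4% for the ordinary two-group interval on the split and 94.8 to 95.1% for the pooled delta-method interval.

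**AUC** (relevant only if a whole-population DAS28ESR AUC is analysed; SD 103 and the 70-unit effect carried over from DAS28CRP). Target: 0.25 × 70 = 17.5 units.

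- Pooled variance: 0.0625 × 4 × 103²/104 + 70² × 0.1875/416 = 25.5 + 2.2 = 27.7, SE 5.26.
- Added term: 0.5625 × 4 × SD²/312 = 6.5, 18.0, 35.3 and 76.5 at responder SD 30, 50, 70 and 103.
- Split SE: 5.85, 6.76, 7.94 and 10.21; ratios 1.11, 1.28, 1.51 and 1.94.

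**Sensitivity to p.** At responder SD 70 the AUC ratio is 1.63 at p = 20% (90/442) and 1.28 at p = 40%. For remission at p = 40% it runs from 1.56 to 1.15 over the same responder rates.

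**Sensitivity to covariate adjustment.**

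| Case | Unadjusted | Covariates explain responder variance only | Same share explained in both groups |
|---|---|---|---|
| AUC, responder SD 70; 20, 40, 50% explained | 1.51 | 1.42, 1.33, 1.28 | 1.50, 1.49, 1.48 |
| Remission, responders 80%; 20, 50% explained | 1.78 | 1.65, 1.44 | 1.77, 1.74 |

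**The case against.** The strongest reply is that little depends on this. The outcomes are exploratory, the planned intervals are valid, and no trial decision changes. The pooled contrast is also nearly the insufficient-responder result rescaled: with 82 completers that difference is 30 ± 19.6 points, and a quarter of it is 7.5 ± 4.9, against 7.5 ± 5.1 once uncertainty in p is included. A reader could obtain it by multiplication. All of that is true. It does not justify the split, which estimates the same quantity with more noise.

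Other points stand as limits. The plan promises no effect scale for these outcomes and does not define HAQ response, so the result applies only where a mean or risk difference is used. Odds ratios, medians and time-to-event measures need separate treatment. Responder values are assumed, and a large gain is not guaranteed. The responder split uses the same minimisation procedure, so the unadjusted half-widths may be somewhat too wide; the adjustment results indicate how far the ratio could move.

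One could add that some outcomes are timed at 28 weeks after randomisation, and that the split supplies the responders' start date. That date survives if the labels are merely ignored: week 32 remains the index visit.

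Finally, the split allows ordinary two-group methods, whereas the replacement can be done wrongly. The fix below therefore names the two likely errors.

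**Conclusion.** The concern holds. For whole-population mean and risk differences, the week-32 split leaves the estimate's target unchanged and adds variance. That a gain exists follows from random halves receiving one treatment scheme. Its size is conditional: at p = 25% without adjustment, split intervals are about 1.3 to 2.0 times as wide for remission (responder remission 70 to 95%) and 1.1 to 1.9 times for AUC (responder SD 30 to 103), if that AUC is analysed at all. This is an efficiency loss in exploratory estimates. It does not introduce bias or affect type I error, and it leaves the primary and main secondary analyses alone. The change is worth making because it is cheap and narrows the intervals that these analyses exist to report.

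**What to change.** For the whole-population intention-to-treat mean and risk differences:

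- Ignore the split labels and use all responders reaching week 32 in both strategy populations.
- Estimate each strategy mean as p × (arm mean among randomised insufficient responders) + (1 − p) × (mean of all responders), so that the contrast is p × (effect among the randomised).
- Define p as randomised insufficient responders divided by those plus the responders reaching week 32. Report patients lost before week 32 separately.
- Use bootstrap or delta-method intervals that allow for the shared responders and for estimating p. Treating the shared responders as independent copies gives an SE of 3.74 instead of 2.6 points at 80% responder remission with 21% dropout.
- Do not simply add all responders to each arm. With 52 + 312 per population, insufficient responders would weigh 52/364 = 14% instead of 25%, and the 7.5-point contrast would shrink to 0.143 × 30 = 4.3.
- State that responders belong to the effectiveness intention-to-treat set. That set is now limited to randomised patients, so dropping the split without saying this would remove them.

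The per-protocol version needs its own p and responder set and is not covered here.

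The cost is a weighted estimator with its own interval method and the protocol amendment that Section 10, Other statistical considerations, requires for a change to the statistical plan. Simple summaries of two non-overlapping populations are given up. The report should say that the pooled contrast is essentially the insufficient-responder effect rescaled to the population, and is not independent evidence.

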In this trial only ARs and adverse events of interest, as defined above, will be captured in the e-CRF.

Following rules apply for reporting adverse events in the e-CRF:

- **After informed consent** has been obtained **but prior to initiation of study treatment**, only SAE of interest and ARs caused by a protocol-mandated intervention should be reported
- **After initiation of study treatment**, all ARs, serious adverse reaction (SARs), SUSARs and (serious) adverse events of interest will be recorded in the e-CRF up to the patient's final study visit.

In the e-CRF all above mentioned events will be detailed with the following information:

- Full details in medical terms and case description
- Duration of the event
- The action taken regarding the event
- The outcome of the event
- *Seriousness criteria (medical judgement of the treating investigator):*
 Seriousness will be evaluated for each adverse event based on the criteria described in the paragraph on definition of a serious adverse event. In case the seriousness is answered "yes" than the event should be reported within 24h.
- *Severity Grading for Adverse Events (medical judgement of the treating investigator):*
 Severity should be graded into one of the three classes that describe the clinical severity of the event as it occurred:
 - Mild (does not interfere with daily living)
 - Moderate (somewhat interferes with daily living or medications needed to relieve event)
 - Severe (incapacitating)
- *Causality grading (medical judgement of the treating investigator)*
 Causality should be graded, to determine to what extent the investigator thinks the adverse event is related to the proposed strategy, prescribed drugs or any other protocol-mandated intervention.
- For serious events: whether the event would be considered expected or unexpected according to the Reference Safety Information, which is the current version of the SmPc. *(medical judgement of the treating investigator)*.
- Outcome

Adverse events and reactions should be followed by the investigator until they have returned to normal or stabilized.

All events related to the normal disease course of RA, which are captured within the outcome parameters of the trial, are not considered as adverse events unless these events are considered by the investigator as adverse events of interest.

Reporting of adverse events that meet seriousness criteria:

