- A **Safety analysis** will include all treated patients, taking into account the treatment that they actually received. Any subject randomized into the study that received at least one dose of study drug will be included for safety analysis.

Statistical analysis plan

Summary of BL data and flow of patients

These BL variables, gathered at initiation of the COBRA-Slim remission induction regimen, will be used to assess comparability of the population eligible for randomization, and they will be reported as proportions or means with their standard deviations, when appropriate.

[figure not shown]

Overview of BL measurements.

Variable	Definition	Measurement level
Age		Continuous
BMI (kg/m ²) at BL	body mass index	Continuous
Gender		Dichotomous
Smoking status at BL	Status never-ever-current	Categorical
Alcohol intake at BL	consumption of any form of alcohol, units per week	Ordinal
Symptom duration at BL	time elapsed between onset of symptoms and BL	Continuous
Disease duration at BL	time elapsed between diagnosis of RA and BL	Continuous
Employed before symptom onset		Categorical
Employed at screening		Categorical
Comorbidities at screening		Categorical
RF positivity at BL	rheumatoid factor	Dichotomous
ACPA positivity at BL	Anti-citrullinated protein antibody	Dichotomous
Erosions present at BL		Dichotomous
Total TJC at BL	tender joint count	Continuous
Total SJC at BL	swollen joint count	Continuous
GA (0-100) at BL	Patient global assessment	Continuous
Pain (0-100) at BL	Visual analog scale of pain	Continuous
Fatigue (0-100) at BL	Visual analog scale of fatigue	Continuous
PhGA (0-100) at BL	physician global assessment	Continuous
ESR (mm/h) at BL	erythrocyte sedimentation rate	Continuous
CRP (mg/l) at BL	C-reactive protein	Continuous
DAS28ESR at BL	28 joint disease activity score (ESR)	Continuous
DAS28CRP at BL	28 joint disease activity score (CRP)	Continuous
HAQ score (0-3) at BL	Health Assessment Questionnaire	Continuous
EQ5D at BL	5 dimensions questionnaire for health-related quality of life	Continuous
RAID at BL	RA impact of disease score	Continuous
PASS at BL	Patient Acceptable Symptom State	Dichotomous

Flow Diagram

All values are an estimation taking into account the distribution present in CareRA. There were 21 failures at screening or randomization (6%) and we expect a drop-out rate of 21%.

Primary outcome analysis

Primary endpoint

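### The whole-population ITT and per-protocol sets leave out patients who start COBRA-Slim and exit before being randomised, and the two safety-set sentences disagree on whether they count

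*Combined protocol and SAP*

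**What the plan says.** Section 10, Subject populations, names two populations. The efficacy population is the insufficient-responder group. For the other, the text reads "The entire group of patients will be called" the effectiveness population, and its purpose is "to investigate the effectiveness of the different schemes in a general RA population as a whole".

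The same analysis sets then apply to each: "For both populations, an intention to treat, a per-protocol and safety analysis will be performed". The ITT analysis "will include all patients randomized into the study", and the per-protocol analysis is a subset of the randomised patients.

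Randomisation comes after treatment has started. Section 3 gives every participant COBRA-Slim at baseline. Insufficient responders are randomised between w8 and w32. For everyone else, Subject populations says that "at week 32 these patients will be randomized to two subgroups that will be further treated identically", each subgroup complementing one of the insufficient-responder arms.

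The safety bullet has two sentences. The first says the analysis "will include all treated patients, taking into account the treatment that they actually received". The second says: "Any subject randomized into the study that received at least one dose of study drug will be included for safety analysis".

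Section 2 asks for all secondary and exploratory objectives in the complete study population as well as in insufficient responders. It lists side effects from baseline to w104 and, for the complete population, sustained remission over BL-w64 and BL-w104. Section 9 states that, once treatment has started, "all ARs, serious adverse reaction (SARs), SUSARs and (serious) adverse events of interest will be recorded in the e-CRF" until the final study visit.

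**The concern.** A patient can be treated for up to 32 weeks without having been randomised. If that patient withdraws consent, is lost or dies in this period, the patient is part of the whole group but meets neither the ITT nor the per-protocol definition. The population and the sets that are meant to analyse it do not match.

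The result is a selection on staying in the trial. Sustained remission counted from baseline would be reported among patients who were randomised as insufficient responders or were still present at w32. It would be presented as describing a general early RA population that started COBRA-Slim. If early leavers do worse than stayers, the reported rate is too favourable.

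For safety, two analysts could build different sets from the same bullet. One would count every treated patient from baseline. The other would count only those later randomised and would lose reactions from the induction period, although the outcome runs from baseline.

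**Working it through.** **The plan's own figures.** From the sample-size table in Section 10:
- 442 screened × 0.94 = 415.5, given as 416 entered.
- 416 × 0.25 = 104 insufficient responders.
- 104 × 0.79 = 82.2, given as 82 completers.
- For a difference of 351 − 281 = 70, SD 103, two-sided alpha 0.05 and 1:1 allocation, the noncentral t gives 86.0% power at 82 and 80.0% at 70. The stated figures are 86% and 80%.

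The figures reproduce. The table goes straight from patients entered to insufficient responders, with no line for patients treated but never randomised.

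**Who falls in which set.**

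| Patient | Whole group | ITT | Per protocol | Safety, first sentence | Safety, second sentence |
|---|---|---|---|---|---|
| Insufficient responder, randomised w8-w32 | yes | yes | if scheme followed | yes | yes, if dosed with study drug |
| Other patient, in the study at w32 and then randomised | yes | yes | if scheme followed | yes | yes, if dosed with study drug |
| Started COBRA-Slim, left before being randomised | yes | no | no | yes | not covered |

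The third row is the problem. For ITT and per protocol the exclusion follows directly from the text. For safety the two sentences give different answers. The second also uses the term study drug without defining it, while Section 8 names only etanercept as the investigational product. An analyst who took the term literally would get a narrower set again.

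**How many patients.** The documents give no loss figure for unrandomised patients before w32, so this is an illustration. Assume that the planned 21% dropout to w104 applies to all entered patients and is spread over the 104 weeks.
- Linear: 0.21 × 32/104 = 6.5% by w32.
- Constant hazard: 1 − 0.79^(32/104) = 7.0% by w32.
- Patients not randomised as insufficient responders: 416 − 104 = 312.
- Affected: 312 × 0.0646 = 20.2 and 312 × 0.0700 = 21.8, so about 20 to 22.
- Assumed range: 312 × 0.02 = 6.2 and 312 × 0.11 = 34.3, so about 6 to 34.

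**What is not touched.** The primary and main secondary outcomes are analysed in randomised insufficient responders only. Their sets, estimates and power do not depend on this point.

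**The case against.** **The safety set is not clearly restricted.** A reader might infer that the safety analysis admits only randomised patients, so that someone with a serious reaction at week 6 who then leaves is counted nowhere. The documents do not support that. The first safety sentence covers all treated patients, and the second does not contain the word only; it can be read as an illustration. What stands is that the two sentences support different sets and the plan does not say which governs.

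**Safety problems alone do not remove a patient.** Section 3 (Treatment failure during study) and Section 6 (Withdrawal of patients) keep patients with serious safety concerns in follow-up. Only withdrawal, loss to follow-up or death ends it. This stands. However, Section 10 expects most dropout to be loss or withdrawal, so the affected group is not empty by design.

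**An ITT set of all randomised patients is normal for an arm comparison.** A never-randomised patient has no arm. Section 2 itself describes the whole-population analyses as the randomised groups, each completed with early responders. This stands for the contrast of the two reconstructed populations. It does not cover single-group statements about the entire group counted from baseline.

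**The size is easily overstated.** Applying 7% to all 416 gives 29, but that includes patients already randomised. The 11% in the plan refers to 28 weeks after randomisation, which is w36 to w60 from baseline; it is not a pre-w32 figure and serves here only as an assumed upper value. A shift in remission rate obtained by counting every leaver as a non-remitter would not match the plan's missing-at-random handling, and the documents give no reaction rate for leavers. No change in whole-population rates can be derived from the documents.

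**The affected outcomes are exploratory.** Section 10 reports them with intervals and without significance claims. True, and this limits the weight of the point.

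**Conclusion.** The concern holds in two parts of unequal strength.

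The ITT and per-protocol sets for the effectiveness population exclude treated patients who leave before being randomised. This is a direct reading of the text. It makes whole-population outcomes counted from baseline conditional on reaching randomisation, and the plan does not say so.

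The safety definition is inconsistent rather than exclusionary. Early leavers' reactions are lost only if the second sentence is taken as the rule.

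About 20 to 22 patients would be affected if the 21% dropout is spread over 104 weeks and applies to the 312 not expected to be insufficient responders; about 6 to 34 if 2% to 11% are lost. The direction of any bias depends on how leavers fare, which the documents do not tell us. The set definitions need correcting whatever the number.

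**What to change.** In Section 10, Subject populations:

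1. Define the safety set once, as all patients who received at least one dose of any protocol treatment from baseline, randomised or not. Remove the randomisation condition from the second safety sentence, and replace the undefined term study drug with protocol treatment.
2. Report whole-population outcomes counted from baseline as single-group summaries in all patients who started COBRA-Slim, and state how many were never randomised.
3. Keep the all-randomised set for the insufficient-responder comparison and for the contrast of the two reconstructed global populations. State that the latter contrast is conditional on randomisation.

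Never-randomised patients should not be placed in both reconstructed arms. That would need a duplication or weighting rule with a matching variance method, and the planned imputation model uses treatment arm and time of randomisation, which these patients do not have. Single-group summaries avoid the problem, though the plan should say how their data after exit are handled.

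The cost is a protocol amendment to the wording and one extra count in the report. Reactions are already recorded in the e-CRF from the start of treatment, so no new data collection is needed. The downside is that whole-population rates may look slightly less favourable.
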